Data Analysis	
Three populations will be defined: (1) The All-Documented Patient Set (APS) consists of all patients with any eCRF documentation. (2) patients with adequately completed recruitment information (Baseline Analysis Set / BAS population); (3) patients having

	
completed 1-year follow-up (Full Analysis Set / FAS population). (4) The Safety Set (SAF) includes all patients who received at least one dose of bemedoic acid and/or bemedoic acid fixed dose combination according to their documentation in the eCRF. For BAS, FAS and SAF binary, categorical, and ordinal parameters will be summarized by means of absolute and percentage numbers within the various categories (including 'missing data' and 'not performed in the center' as valid category at baseline). Numerical data will be summarized by means of standard statistics (i.e. number of available data, number of missing data, mean, standard deviation, minimum, median, maximum, lower and upper quartile).
 
At the final analysis the differences in the CV risk score for Very High Risk and for High Risk patients will be calculated.
 
In addition, adequate graphs (e.g. bar charts, box-whisker plots) may be presented to summarize the results for some parameters.
 
Analysis of changes in numerical parameters (as the differences in Score risk between baseline and 1-year follow up) will be done by paired Wilcoxon signed rank test and paired t-test if assumptions of parametric tests will be met. Comparison of these 1-year changes between subgroups will be done by Kruskal-Wallis test and ANOVA test if assumptions of parametric tests will be met. Also adjusted analyses for age, sex and country effects will be done.
 
Time-to-event variables will be analyzed via a Cox proportional hazard regression model presenting hazard ratios and the corresponding 95% confidence intervals. Additionally, adjusted Cox models for age, sex and country effects will be presented. In addition, Kaplan-Meier curves will be presented for time-to-event variables. Two-sided 95%-CI will be presented for important parameters, but should be interpreted in an exploratory descriptive way.
 
All statistical testing (including hazard ratios, relative risks etc.) will be performed in an exploratory manner only. Details regarding statistical analyses will be described in the SAP and in the statistical section of the report.

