### 8.2 Secondary Objectives

The secondary effectiveness objectives are to document:

- The relationship between the above-mentioned treatment modalities and plasma levels of other potentially ASCVD-modifying cholesterol fragments, namely HDL-C, non-HDL-C, TC, apoB, TGs, and Lp(a).
- Changes in the inflammatory marker hsCRP over time  
Changes in the patient's overall CV risk assessment over time measured through CV risk score calculators

The secondary safety objectives are to document:

- Clinical events associated with the various treatment modalities:
  - Laboratory abnormalities
  - Muscle-associated symptoms
  - New onset and/or worsening diabetes
  - Changes in the patients' glycemic status over time
  - Adverse Drug Reactions associated with bempedoic acid and/or fixed dose combination with ezetimibe

Additional secondary objectives are to document:

- The characteristics of the sites and physicians caring for Very High Risk and High Risk patients
- The patients' use of lipid-modifying treatment, especially with regard to a switch from one drug class to another, a dose modification of a given drug, a switch from one statin to another, any evidence of statin intolerance or insufficient responsiveness to a statin, including a maximally tolerated statin, and any use of combination drug therapy
- Various HEOR parameters associated with the management of dyslipidemic patients, such as PRO and healthcare resource use.

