**Study population:**

The study population consists of Very High Risk and High Risk dyslipidemic patients previously diagnosed and treated as well as newly treated patients receiving their first LMT. At baseline data collection point, baseline characteristics (LDL-C and other lipid parameters, CV risk assessment, concomitant diseases such as diabetes and congestive heart failure, certain HEOR variables) and relevant medical history (CV events such as myocardial infarction and stroke) will be documented.

In addition, for the previously diagnosed and treated patients, details on the lipid modifying treatment during the year before enrolment will be collected.

This information will be collected from the patients' chart from all dyslipidemia-related visits at which the patient has been seen by the physician, starting from date of diagnosis.

At the follow-up data collection point at 1 year ( $\pm$  2 months), available information on the patients' routine management between baseline and this data collection point, and efficacy and safety variables will be collected: LDL-C and the other lipid parameters, inflammatory status, overall CV risk scores (SMART and Framingham risk scores will be calculated centrally based on collected patient information), CV events such as myocardial infarction and stroke, diabetes related parameters, renal function parameters, and the lipid-modifying therapy. As an optional assessment, PRO questionnaires will be completed by the patient preferably in the physician's office.

Electronic data capture (EDC) will be used for the recording of the information.

As this is a non-interventional study, only data that is based on routine clinical practice will be documented. Treatment pattern and treatment initiation, continuation or changes are solely at the discretion of the physician and the patient. There will be no attempt to influence the prescribing patterns of any individual treating physician. All medication will be prescribed according to usual standard of care and will not be provided by the study sponsor. Participation in the study will in no way influence payment or reimbursement for any treatment received by patients during the study.

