### **Schedule**

The total study period from FPI to LPO is 30 months. The individual start per country depends on the approval status of the protocol by the responsible Ethics Committee and Competent Authorities and will range approximately from Q3 2019 to Q4 2020. Per country, the patient recruitment period consists of 9 months, followed by a 12-month follow-up period per patient. It is expected that the last patient will complete the study in Q4/2021. The final study report is expected to be available in Q4/2022.

Patients eligible for the study at the site will be documented in a screening log to allow for judgement on representativeness of patient inclusion.

Patient data will be documented at two data collection points in time:

- Baseline at enrolment,
- FU1 approximately  $12 \pm 2$  months after baseline (face-to-face meeting preferred)

At baseline, the patients' medical history will be documented as well as the currently applied therapy. At the annual follow-up data collection point, changes in therapy and disease status since the last data collection point will be documented. At the baseline and the follow up data collection point the patients will be asked to complete the patient reported outcome (PRO) questionnaire EQ-5D-5L and the PAM-13 questionnaire.

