Numerical data will be summarised by means of standard statistics (i.e. number of available data, number of missing data, mean, standard deviation, minimum, median, maximum, lower and upper quartile). In addition, adequate graphs (e.g. bar charts, box-whisker plots) may be presented to summarize the results for some parameters. Analysis of changes in numerical parameters (as the differences in Score risk between baseline and 1-year follow up) will be done by paired Wilcoxon signed rank test and paired t-test if assumptions of parametric tests will be met. Comparison of these 1-year changes between subgroups will be done by Kruskal-Wallis test and ANOVA test if assumptions of parametric tests will be met. Also adjusted analyses for age, sex and country effects will be done. Time-to-event variables will be analyzed via a Cox proportional hazard regression model presenting hazard ratios and the corresponding 95% confidence intervals. Additionally, adjusted Cox model for age, sex and country effects will be presented. In addition, Kaplan-Meier curves will be presented for time-to-event variables. Two-sided 95% confidence intervals will be presented for important parameters, but should be interpreted in an exploratory descriptive way.

Depending on the variable(s) of interest, additional selection criteria for patients (e.g. subgroup analyses) considered in specific analyses may be used, if considered useful during the statistical

analysis. Details on the selection criteria used will be given in the Statistical Analysis Plan (SAP) and in the statistical section of the report.

The statistical analysis will be performed using SAS version 9.4 or higher

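### The 1-year change in SMART and Framingham scores may combine management with a year of ageing; an age-fixed change should be reported beside it

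*Combined protocol and SAP*

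**What the plan says.** Section 8.2 of the observational plan lists, among the secondary effectiveness objectives, the documentation of "Changes in the patient's overall CV risk assessment over time measured through CV risk score calculators". Section 9.2 (Study population) names the scores for the follow-up data collection point: "SMART and Framingham risk scores will be calculated centrally based on collected patient information". Section 8.1 pairs SMART with Very High Risk patients and Framingham with High Risk patients, as examples. The Summary (section 4) adds: "At the final analysis the differences in the CV risk score for Very High Risk and for High Risk patients will be calculated".

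For the analysis, section 9.7 states: "Analysis of changes in numerical parameters (as the differences in Score risk between baseline and 1-year follow up) will be done by paired Wilcoxon" test, with a paired t-test if its assumptions are met. One-year changes are compared between subgroups by Kruskal-Wallis or ANOVA. On age it says only: "Also adjusted analyses for age, sex and country effects will be done".

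The Schedule gives nine months of recruitment per country, "followed by a 12-month follow-up period per patient", with a window of 2 months either side. The Patient Groups section rules out comparator groups. Section 9.7 calls all analyses exploratory and leaves detail to a separate SAP, which is not part of the text reviewed. No section lists the inputs to either score or says whether the follow-up score uses age at baseline or age at follow-up. The limitations in section 9.9 do not mention ageing.

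**The concern.** A score that contains age, recalculated a year later with the new age, rises even when lipids, blood pressure and treatment are unchanged. The paired test then compares the sum of the management effect and the ageing step with zero. No untreated or unchanged group is available from which to estimate and subtract the ageing step.

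The planned age adjustment looks like a remedy but is not one for the mean change. It handles differences in age between patients. The ageing step is about the same year within every patient, so it stays in the adjusted mean.

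Because the objective is listed under effectiveness, readers will tend to take the change as a result of lipid management. With some 8000 patients, even a modest drift would also look highly significant.

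**Working it through.** **Inputs from the plan (section 9.5).** The assumed LDL-C fall is 0.9 mmol/L. The precision for the relative risk of major vascular events is ±13% absolute and ±16% relative.

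**Inputs that are assumptions.** Age is an input to both scores and is updated at follow-up. Score hazard rises by a factor g of 1.03 to 1.09 per year of age. The baseline score is 20%. The score responds to LDL-C along the slope implied by section 9.5. That slope describes major vascular events rather than either calculator, so it serves only to set a scale.

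**Step 1: the plan's own figure.** Absolute over relative precision gives an implied relative risk of 0.13/0.16 = 0.8125 for 0.9 mmol/L. Rounding allows 0.125/0.165 = 0.76 to 0.135/0.155 = 0.87. The two stated precisions are consistent with each other. They cannot be rebuilt from event counts, because no event rate or group split is given.

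**Step 2: formulas.** With a 20% baseline score, the follow-up score is 1 - 0.8^(g × h), where h = 0.8125^(d/0.9) for an LDL-C fall of d mmol/L. Setting g = 1 gives the age-fixed score. The fall that just cancels one year of ageing is 0.9 × ln(g) / -ln(0.8125).

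**Step 3: results (changes in percentage points).**

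| Rise per year of age | Ageing alone | Net change, fall 0.9 | Share of improvement lost | Net change, fall 0.2 | Cancelling fall (mmol/L) |
|---|---|---|---|---|---|
| 3% | +0.53 | -2.97 | 0.45/3.42 = 13% | -0.29 | 0.13 |
| 5% | +0.89 | -2.67 | 0.75/3.42 = 22% | +0.05 | 0.21 |
| 9% | +1.59 | -2.07 | 1.35/3.42 = 39% | +0.73 | 0.37 |
| Age fixed | 0 | -3.42 | none | -0.81 | none |

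Across the rounding range of the implied relative risk, the cancelling fall runs from 0.10 (3%, relative risk 0.76) to 0.56 mmol/L (9%, relative risk 0.87). The 0.2 mmol/L column is an illustration; that fall is not in the plan.

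**Step 4: does adjustment for age help?** A simulation of 8000 patients used assumed ages with mean 65 and SD 10, g = 1.05, and LDL-C changes with mean -0.1 and SD 0.6 mmol/L. The raw mean change was +0.61 points (Wilcoxon p < 0.001). After linear adjustment for age, sex and country, evaluated at the average patient, it was still +0.61. With age fixed it was -0.31. Adjustment at the covariate means leaves the mean change where it was.

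**Step 5: would the drift be detected?** Take a drift of 0.9 points and an assumed SD of the change of 10 points. The standard error with 8000 patients is 10/√8000 = 0.112, so z is about 8. For SDs of 5 and 15, z is about 16 and 5.4.

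**The case against.** The strongest answer is that the plan sets out to document overall CV risk, and overall risk properly includes age. On that reading the attained-age change is the right quantity, and modifiable risk is a different objective that the plan never states. This stands. It means that the attained-age change need not be demoted. It does not tell a reader how much of the change is due to management, which is what a listing under effectiveness invites.

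Second, the premise is not documented. Neither the score inputs nor the age used at follow-up is given. Table 1 marks baseline characteristics at baseline only, although attained age could be derived from dates. This also stands. A reader might infer that the analysis as planned definitely includes ageing and understates any improvement, but the text leaves the derivation open and supports only a conditional statement.

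Third, a reader might infer that the analysis will show rising risk where modifiable risk has fallen. At the plan's own 0.9 mmol/L it does not. The sign changes only for small falls, and the threshold depends on assumed ageing rates and a slope back-solved from two rounded percentages.

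Fourth, a reader might infer that subgroup comparisons are distorted by different age mixes. The planned age-adjusted analyses address at least part of that. Drift could still differ between risk strata if each is scored with its own calculator, but the documents do not allow that to be sized.

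Finally, the analysis is secondary and exploratory, detail is deferred to the SAP, and LDL-C, which the primary objective concerns, is unaffected. That limits the severity. It does not remove a systematic shift, and section 9.7 allows the SAP to be finalized as late as just before database lock.

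**Conclusion.** The point holds conditionally. If age is an input to the scores and is updated at follow-up, the planned paired change combines management with about one year of ageing. Neither the absence of a comparator nor the covariate adjustment for age allows the two to be separated.

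Under the stated assumptions, the shift at a 20% baseline score is about 0.5 to 1.6 percentage points. At the plan's assumed LDL-C fall this attenuates the improvement by roughly 13% to 39% and leaves its sign intact. Reversal is plausible only where falls are below about 0.13-0.37 mmol/L (0.10-0.56 allowing for rounding), for example in previously treated patients whose treatment changes little.

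The consequence is for interpretation of one secondary objective, not for sample size or error rates. The documents do not support calling the attained-age change wrong for overall risk, or requiring the age-fixed change to replace it.

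**What to change.** In section 9.7 and the Summary:

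- State which age enters the follow-up score.
- Prespecify a second change, with age held at its baseline value in both calculations, and report it beside the attained-age change. Label the latter as overall risk including ageing; it can remain the answer to the objective in section 8.2.
- Base any statement about the effect of management on the age-fixed change. It is still an uncontrolled before-after difference and should be described as such.

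In section 9.9, name ageing as a limitation of the score change.

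The cost is one extra derived variable, a second reported result and some wording. The scores are already calculated centrally from collected inputs, so no new data, visits or patients are needed. If the sponsor already intends to hold age fixed, one sentence saying so settles the ageing question, and the attained-age change should then be added for the overall-risk objective.

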## 6 MILESTONES

- Start of data collection: Q1/2020
- Planned snapshots: 2 for baseline data, 2 for follow-up data
- Planned end of data collection (planned): Q4/2021
- Final report of study results (planned): Q4/2022

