### 9.2 Setting

Approximately 8000 patients from different care settings (primary care and secondary care, different specialties) will be enrolled consecutively at a total of approximately 800 sites. It is estimated that each site will contribute 10 patients, although additional patients - subject to approval - may be considered. At each study site, the patients will be enrolled consecutively. Patients will be stratified for High and Very High Risk (per physicians' assessment) as well as for previously and newly treated patients. Sites will be required to complete a patient screening log of eligible patients for this disease registry at their treatment centers. This log will document

how patients came to be included or excluded from the study, in order to assess the representativeness of the study population. Minimal information will be recorded for all patients who are screened for study enrolment, but no patient-identifiable information should be recorded. Those patients who provide their informed consent will be enrolled into the study.

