## 9.7 Data Analysis

This section describes the most relevant parts of the statistical analyses planned for a NIS/registry. All statistical methodology will be described in detail in the Statistical Analysis Plan (SAP) which will be finalized at the latest prior to database lock. All variables collected in the CRFs and/or other recordings (if applicable) and all derived parameters will be used in the statistical analysis.

A report including descriptive statistics of all documented parameters will be generated also if required for each participating country. Details on the selection criteria used will be given in the SAP and in the statistical section of the report.

Referring to the primary objective, the statistical analysis will be performed in a purely explorative descriptive way according to DSE SOP R-440.

Data will be collected at the following data collection points

- baseline ,
- 1-year prospective follow-up

Following analysis sets will be used for analysis

- The All-Documented Patient Set (APS) consists of all patients with any eCRF documentation.
- The Baseline Analysis Set (BAS) consists of all eligible patients of the APS who provide adequate baseline information.
- The Full Analysis Set (FAS) consists of all patients from the BAS with available 1-year follow-up data.
- The Safety Set (SAF) includes all patients who received at least one dose of bempedoic acid and/or bempedoic acid fixed dose combination according to their documentation in the eCRF.

No primary endpoint was defined in this study. No formal statistical tests will be performed within the statistical analysis.

All statistical analyses will be performed in a purely exploratory descriptive way.

Binary, categorical, and ordinal parameters will be summarized by means of absolute and percentage numbers within the various categories (including 'missing data' as valid category at baseline).

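### The adjusted analyses name only age, sex and country, and the plan's own strata enter no described model, so a comparison of lipid change by treatment modality could reflect the share of newly treated patients

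*Combined protocol and SAP*

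**What the plan says.** Section 9.7 and the Data Analysis row of the Summary (section 4) give the same adjustment set twice. For 1-year changes: "Also adjusted analyses for age, sex and country effects will be done". For time-to-event variables, section 9.7 has: "Additionally, adjusted Cox model for age, sex and country effects will be presented". The unadjusted comparison is described as "Comparison of these 1-year changes between subgroups will be done by Kruskal-Wallis test and ANOVA test", without saying which subgroups. The Cox paragraph promises hazard ratios without naming an exposure. Section 9.7 also leaves room for more: "additional selection criteria for patients (e.g. subgroup analyses) considered in specific analyses may be used".

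Section 9.2 states: "Patients will be stratified for High and Very High Risk (per physicians' assessment) as well as for previously and newly treated patients". The Summary and the eligibility criteria repeat this. In the analysis text, risk category appears once: the Summary gives CV risk score differences for each risk stratum. Previously/newly treated status appears in no analysis sentence.

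The secondary objectives (section 8.2) cover the relation of treatment modalities to lipid levels, and "Clinical events associated with the various treatment modalities". Under section 9.2, physician and patient choose treatment, no comparator groups are planned, and the newly treated are patients starting lipid-modifying therapy for the first time. Section 9.9 warns that wrongly recorded treatment changes could misclassify exposure. It does not mention confounding by indication.

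**The concern.** Treatment is not randomised. Someone starting a first lipid-modifying therapy is likely to show the LDL-C fall of initiation over the next year. In a patient already on therapy, the 1-year change reflects continuation or modification. Two modalities that work equally well, but are used in different proportions of new starters, would then show different mean changes. The same reasoning applies to events if one modality is used more in Very High Risk patients.

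The plan treats these two factors as important enough to classify every patient by them, yet its stated covariates leave both out. Adjustment for age, sex and country helps only as far as those variables track treatment history and risk category. At stake is whether a published adjusted difference in lipid change between modalities, with its confidence interval, can be read as anything but case mix.

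**Working it through.** **Plan figures.** The plan gives no figure for this point: no modality group sizes, SD of LDL-C change, share newly treated or event rate. The inputs below are assumptions, except the total of 8000 and the 0.9 mmol/L LDL-C reduction (section 9.5) and the country list (section 9.2).

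**Spurious difference in LDL-C change.** For two equally effective groups, bias = (difference in share newly treated) × (difference in mean change, new minus previous).
- 0.05 × 0.3 = 0.015 mmol/L
- 0.10 × 0.6 = 0.06 mmol/L (0.06/0.9 = 7% of the plan's assumed reduction)
- 0.20 × 0.9 = 0.18 mmol/L (0.18/0.9 = 20%)
- 0.30 × 1.3 = 0.39 mmol/L

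**Against sampling error.** The 95% CI half-width is 1.96 × SD × √(2/n), with SD 1.0 and n per group. The bias passes it when the difference in share exceeds half-width ÷ difference in mean change.

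| n per group | Half-width (mmol/L) | Points needed at 0.3 / 0.6 / 0.9 / 1.3 mmol/L |
|---|---|---|
| 500 | 0.124 | 41.3 / 20.7 / 13.8 / 9.5 |
| 1000 | 0.088 | 29.2 / 14.6 / 9.7 / 6.7 |
| 2000 | 0.062 | 20.7 / 10.3 / 6.9 / 4.8 |

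**Does the stated adjustment help?** A simulation used 8000 patients, 14 countries, 200 runs and no true modality effect. Newly treated patients fell 1.0 mmol/L more, and their share was 11% in one modality and 30% in the other. The modality difference was 0.19 mmol/L unadjusted, 0.19 after age, sex and country, and 0.00 once treatment history was added. Age was only weakly related to treatment history, and sex and country not at all, so it shows that the three covariates need not remove the bias. If country tracks treatment history in practice, they would remove part of it.

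**Cox models.** If Very High Risk patients have k times the event rate and make up shares p1 and p2 of two equally effective groups, the spurious hazard ratio is about (p1·k + 1 − p1)/(p2·k + 1 − p2).
- 80% vs 70%, k = 1.5 / 2 / 3: 1.04 / 1.06 / 1.08
- 80% vs 60%, k = 1.5 / 2 / 3: 1.08 / 1.13 / 1.18

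The 95% CI factor with two equal groups is exp(1.96 × √(4/events)). With 2%, 5% or 10% of 8000 having an event (160, 400, 800), it is 1.36, 1.22 or 1.15. Only the largest case (1.18) passes it, and only at 10%. With a 20:80 split and 800 events the factor is exp(1.96/√(800 × 0.16)) = 1.19, and even that case falls below.

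**Cost of adding treatment history.** SE inflation = √(1/(1 − R²)) − 1, with R² = d²·q(1 − q)/(p(1 − p)). Here d is the difference in share newly treated, q the fraction of patients in the group with the higher share, and p the overall share.
- q = 0.5: 0.2 vs 0.1, 1.0%; 0.1 vs 0, 2.7%; 0.4 vs 0.1, 6.6%; 0.3 vs 0, 10.2%
- q = 0.2: 0.3 vs 0, R² = 0.255, 15.9%

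**Model terms.** Twelve named countries plus one to three more make 13 to 15, hence 12 to 14 country terms. Age (linear) and sex bring this to 14 to 16; two more make 16 to 18.

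**The case against.** The strongest reply is that no comparison by modality is planned. The objectives are to document, no comparator groups are foreseen, everything is labelled exploratory, and the subgroups might be the strata themselves. A covariate set cannot be judged until the exposure is known. This stands in part: a reader might infer a committed between-modality test, and the documents do not support that. But section 9.7 promises subgroup comparisons, hazard ratios and adjusted results, section 8.2 relates modality to lipids and events, and section 9.9 speaks of exposure when discussing treatment changes. An exploratory label limits the claims made; it does not remove bias from a reported adjusted estimate.

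A reader might also take the Summary's CV risk score sentence as a Very High versus High Risk contrast left unadjusted for treatment history. It is better read as change over time within each stratum: section 8.1 gives SMART as the example score for one stratum and Framingham for the other, and two different scores are not naturally contrasted.

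Stratification may already mean separate reporting. That is plausible without randomisation, but no analysis sentence says so beyond the CV risk score. A related objection has force: if the modality effect differs between new starters and continuing patients, one additive term averages over the difference, and stratified results show it better.

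Finally, the full methodology is deferred to a SAP whose content is not in these documents, and it may add covariates. The finding is therefore about what this plan specifies. A reader might go further and infer that covariates will be picked after follow-up data are seen, because section 6 lists "Planned snapshots: 2 for baseline data, 2 for follow-up data". No dates or contents are given for those snapshots, so that cannot be concluded.

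**Conclusion.** The point holds in conditional form. The plan names an adjustment set of age, sex and country and leaves its own two strata out of every described model. If lipid changes are compared by modality, unequal shares of newly treated patients can produce an apparent difference in effectiveness that the stated covariates need not remove.

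The size is unknown. On assumed inputs it runs from 0.015 to 0.39 mmol/L, with 0.06 mmol/L as a moderate illustration. Whether it exceeds sampling error depends on group size and on both inputs. The case is mainly about lipid change. A reader might infer that the hazard ratios would be materially distorted as well, but on these figures that bias is probably below sampling error. The change is worth making because the plan already requires both factors to be known for every patient and the cost is small.

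**What to change.** In section 9.7 and the Summary:

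1. Report 1-year changes in LDL-C and the other lipids by risk category and by previously/newly treated status, alongside the pooled figures.
2. Replace the adjustment wording with, for example: adjusted analyses of 1-year change will include risk category and previously/newly treated status in addition to age, sex and country, except where that factor is itself the subgroup compared; for consistency, adjusted Cox models will include the same factors.

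In section 9.9:

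3. State that residual confounding by indication remains. Risk category rests on the physician's assessment, and baseline LDL-C, diabetes and intolerance would still be unadjusted.

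The cost is wording in the plan and the SAP, some extra tables, and two more model terms. The standard error of the group difference rises by about 1% to 10% with equal groups and about 16% in the unbalanced example, before any gain from lower residual variance.
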